2.2. Randomization

The methodology of the study involved the use of randomization to distribute participants into groups. Randomization was block-based. All blocks were balanced, i.e., each block should have an equal number of participant numbers with 2 types of preventive treatment.

2.3. Blinding procedure

This study is open-label.

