3. EVALUATION OF EFFECTIVENESS PARAMETERS

3.1. Endpoints of the study

The primary criterion of effectiveness is the proportion of patients with acute respiratory viral infections, including COVID-19, at the end of the period of preventive administration of the drug (measurement time: 28 days).

The scientific hypothesis is that the prophylactic administration of Ingaron will lead to a decrease in the incidence of acute respiratory viral infections, including COVID-19, among adult volunteers.

The preventive efficacy of the study drug will be evaluated by the following primary and secondary endpoints.

Primary endpoint:

The proportion of patients with acute respiratory viral infections, including COVID-19, at the end of the period of preventive administration of the drug (measurement time: 28 days).

Secondary endpoints:

1. The proportion of patients with confirmed COVID-19 at the end of the period of preventive treatment of the drug (measurement period: 28 days).
2. The proportion of patients with acute respiratory viral infections, including COVID-19, at the end of the follow-up period (change period: 2 months).
3. The proportion of patients with confirmed COVID-19 at the end of the follow-up period (change period: 2 months).
4. Frequency of development of complicated course of ARVI.
5. The proportion of participants with each of the scores (0-8) according to the WHO Clinical Improvement Scale (change period: 28 days).
6. The proportion of participants with each of the scores (0-8) according to the WHO Clinical Improvement Scale (change period: 2 months).
7. Duration of symptoms of the disease of study participants who had acute respiratory viral infections, including COVID-19 (change period: 2 months).
8. The duration of the symptoms of the disease of the study participants who were infected with ARVI, including COVID-19 (measurement period: 28 days).

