3.2. Registration, analysis and evaluation of effectiveness parameters

The effectiveness will be evaluated based on the data obtained during the study visits. The effectiveness assessment will include the presence of a case of ARVI, including COVID-19.

Confirmation of clinical cases of ARVI, including COVID-19:

In the following cases:

- 1) a positive result of PCR on SARS-CoV-2 RNA, regardless of the presence of clinical symptoms;
- 2) appearance of clinical symptoms of ARVI in the absence of a PCR result on SARS-CoV-2 RNA or in the case of a negative result on SARS-CoV-2 RNA, -

at any stage during participation in the study, a completion visit (Visit 3) is conducted at the end of the quarantine period (at least 14 days from the date of signing Consent for the treatment of a new COVID-19 coronavirus infection in

outpatient settings (at home) and compliance with the isolation regime or discharge from the hospital in case of laboratory confirmation of COVID-19), at which the patient returns the participant's diary and reports his condition to the doctor-researcher, transmits information about hospitalization, duration of symptoms, results of tests and performed studies.

Definition of the COVID-19 case:

Suspicious case of COVID-19

Body temperature above 37.5 ° in addition to one or more of the following signs (in the absence of other known causes that explain the clinical picture, regardless of the epidemiological history):

- Cough (dry or with scant sputum)
- Shortness of breath
- Feeling of congestion in the chest
- SpO₂ no more than 95%
- Sore throat
- Nasal stuffiness or moderate rhinorrhea
- Smell disorders or anosmia
- Ageusia
- Conjunctivitis
- Fatigue
- Myalgia
- Headache
- Vomiting
- Diarrhea
- Skin rash

Probable case of COVID-19

Body temperature above 37.5° in addition to one or more of the following signs:

- Cough (dry or with scant sputum)
- Shortness of breath
- Feeling of congestion in the chest
- SpO₂ no more than 95%
- Sore throat
- Nasal stuffiness or moderate rhinorrhea
- Smell disorders or anosmia
- Ageusia
- Conjunctivitis
- Fatigue
- Myalgia
- Headache
- Vomiting
- Diarrhea
- Skin rash

In the presence of at least one of the epidemiological signs:

- Return from cross-border travel 14 days before the onset of symptoms

- The presence of close contacts over the past 14 days with a person under surveillance for COVID-19, who subsequently became ill

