In the case of ARVI symptoms characteristic of a suspicious case of COVID-19, accompanied by a negative result of PCR test, registered during or after a preventive course (during the period of participation in the study after randomization until the end of the observation period), the patient may additionally undergo a quantitative test for the presence of IgM and IgG antibodies to SARS-CoV-2 by the ELISA method for the purpose of additional verification and detection of COVID-19 cases. An additional quantitative test for antibodies to SARS-CoV-2 can be performed from the 10th to the 21st day after the appearance of the first symptom of ARVI to register the immune response of the acute phase of infection at the beginning of its development (increased IgM levels) or during high-grade response (increased IgM and IgG), considering the seronegative the period of the disease (5-7 days). The analysis is taken only in the absence of fever and a satisfactory general condition of the patient, accompanied by a favorable recovery dynamic. When interpreting the results, it is necessary to consider the probability of obtaining false positive results (for example, the presence of "cross-reacting" antibodies). If the interpretation of the results is difficult, it is allowed to conduct a repeated ELISA study using the same test systems after 5-7 days to assess the dynamics of indicators. Quantitative determination of IgM and IgG antibodies in the blood by the ELISA method will be carried out with the support of DiaLab LLC Plus."

The condition of the study participant is assessed according to the WHO standard scale of clinical improvement from 0 to 8 points at each visit, including a phone call visit. In case of registration of ARVI at the final visit 3, in parallel with the current assessment of the participant's condition, an additional assessment of the case is carried out according to the WHO scale, reflecting the maximum clinical manifestation of the disease.

WHO Clinical Improvement Scale

Assessment on the WHO scale	0	1	2	3	4	5	6	7	8
Select the appropriate score from 0 to 8	Not infected	Outpatient		Hospitalized with mild form					Died
	there are no clinical	no activit	activity restrict	hospitalized, no	hospitalized, oxygen	non-invasive lung	endotracheal	ventilation + additional	death

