5. STATISTICAL DATA PROCESSING

5.1. Statistical methods of analysis

To create conditions for an independent evaluation of the results obtained, statistical data processing at the end of the study will be carried out by employees who are not related to the management of the subjects participating in the study. The primary data base was created in Excel when processing registration cards received from the clinical center. Data processing will be performed in the software environment of the R package (R: A language and environment for statistical computing. R Core Team. R Foundation for Statistical Computing, Vienna, Austria)⁶ version 4.1.0 using "A Guidance Document for the Use of R in Regulated Clinical Trial Environments"⁷.

Descriptive statistics are presented for all baseline indicators collected during the study for all subjects included in the study (safety-population). The distribution of subjects, demographic and initial characteristics are presented using descriptive statistics methods.

For numerical indicators, such as demographic and anthropometric data (body weight, age, height, BMI), as well as numerical performance parameters will be calculated:

- Number of missing values (N);
- Minimum value (Min);
- Maximum value (Max);
- Arithmetic Mean (M);
- Standard Deviation (SD);
- Median (Me).

For qualitative variables (frequency of AE/SAE development, for example), absolute number in the n/N format will be given, as well as the percentage (%).

Verification of the normality of the distribution will be carried out by one of the generally accepted methods (visualization of data in a dot diagram in combination with the calculation of the Kolmogorov-Smirnov test, as well as the test for asymmetry and kurtosis).

In the case of a normal distribution, an intergroup comparison of quantitative characteristics will be carried out using the t-test (or the Mann-Whitney test otherwise). For categorical data, the χ^2 -criterion or the exact Fisher test will be applied if the expected frequency in any of the cells is less than 5.

If statistically significant differences between the groups are found, the magnitude of the differences between the study groups will be estimated using confidence intervals. Significance levels and confidence intervals will be calculated as two-sided, and the statistical significance of the differences is by default two-sided and refers to a significance level of 0.05.

Correction for multiple comparisons is not required.

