5.5. Populations of participants for analysis

The following populations will be formed for analysis: ITT, PP and safety; additionally: ITT_NV, PP_NV, ITT_NV_BE, PP_NV_BE.

Statistical data analysis will be carried out in the following populations of participants:

1. Population of all included and randomized participants (intention-to-treat, ITT): all randomized participants who were exposed to the study drug, regardless of the degree of protocol compliance during the study. This data set is the main one for the analysis of primary and secondary effectiveness parameters;
2. Population of participants who completed the study according to the protocol (per protocol, PP): all randomized subjects who completed participation in the study in accordance with the protocol (completed the prescribed period of treatment and follow-up without significant deviations from the protocol). This data set is additional for the analysis of primary and secondary effectiveness parameters;
3. Safety population: The data set analyzed for safety assessment is identical to the ITT data set. However, unlike the population depending on the prescribed treatment, participants are analyzed depending on the actual treatment (if it differs from the treatment that was prescribed by randomization). All types of safety analysis will be based on the use of a data set for security assessment;
4. Modified population of all included and randomized participants (intention-to-treat, ITT) not vaccinated against COVID-19: ITT_NV. This data set is additional for the analysis of the primary efficiency parameter;
5. Modified population of participants who completed the study according to the protocol (per protocol, PP), not vaccinated against COVID-19: PP_NV. This data set is additional for the analysis of the primary efficiency parameter;
6. Modified population of all included and randomized participants (intention-to-treat, ITT) not vaccinated against COVID-19 or vaccinated before inclusion in the study: ITT_NV_BE. This data set is additional for the analysis of the primary efficiency parameter;
7. Modified population of participants who completed the study according to the protocol (per protocol, PP), not vaccinated against COVID-19 or vaccinated before inclusion in the study: PP_NV_BE. This data set is additional for the analysis of the primary efficiency parameter.

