Thus, the safety population will be used to present demographic data about participants, as well as for safety assessment. ITT will be considered the main sample for comparative analysis of performance parameters. The PP population will include only participants who completed the study without critical deviations from the protocol and will be formed as an additional sample to evaluate the effectiveness parameters in order to analyze the sensitivity of the results obtained in the ITT population. The modified populations will be used to perform sensitivity analysis when evaluating the primary endpoint.

The number of participants who must complete the study in accordance with the protocol is 286 in each group, or a total of 572 participants.

The number of randomized participants is 315 in each group or total of 630 participants.

The number of screened participants is up to 642.

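### SAP 2.3 says only that the study is open-label, so ARVI case status and judgement-based per-protocol exclusions can be settled with arm and outcome in view

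*SAP*

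**What the plan says.** SAP 2.3 consists of one sentence: "This study is open-label". The only related safeguard is in SAP 5.1, where statistical processing "will be carried out by employees who are not related to the management of the subjects participating in the study". Neither document provides for a masked assessor, an adjudication step or a blind data review.

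The site knows the arm. Under the Protocol's section on randomization of study participants, the researcher is told the group number by phone. The two arms also use different diaries (Protocol Appendices 1 and 2). At Visit 3 the participant "reports his condition to the doctor-researcher" (SAP 3.2).

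The following decisions leave room for judgement:

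- **ARVI case.** SAP 3.2 counts clinical symptoms of ARVI when the PCR is negative or absent, and sets no symptom threshold.
- **COVID-19 class.** The suspicious class applies "in the absence of other known causes that explain the clinical picture". After a negative PCR, "the patient may additionally undergo a quantitative test" for antibodies, which can move a case to confirmed.
- **Complicated course.** "Frequency of development of complicated course of ARVI" is secondary endpoint 4 in SAP 3.1. No criterion is given, and the sub-rows of SAP Table 12 are blank.
- **PP membership.** One sentence of SAP 5.5 admits those who "completed the prescribed period of treatment and follow-up without significant deviations from the protocol"; a later one admits "only participants who completed the study without critical deviations from the protocol". Neither kind of deviation is listed. Of the Protocol's exclusion criteria, number 4 (systematic non-compliance with procedures) and number 6 (a condition that the researcher thinks may distort results) also need judgement.

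**The concern.** Without a placebo, participants and investigators cannot be masked, and that is not the complaint. Decisions made afterwards on the recorded data can be masked, and the SAP does not ask for it. Someone who knows the arm may read a doubtful PCR-negative illness, or a doubtful deviation, differently in the two groups, and the error could favour either arm. SAP 5.5 uses PP to test the sensitivity of the ITT result, so the same knowledge can act on the main result through ARVI status and on its check through PP membership.

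**Working it through.** **1. The planned outcome.** The Protocol's formula with 5% v 2% and t = 1.96 is

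n = (0.05 × 0.95 + 0.02 × 0.98) × 1.96² / 0.03² = 0.0671 × 3.8416 / 0.0009 = 286.4.

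Multiplying by 1.10 gives 315.05. Both match the stated 286 and 315 per group. Expected cases at 286 are 0.05 × 286 = 14.3 and 0.02 × 286 = 5.7, or about 14 v 6.

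**2. One case near that outcome.** SAP 5.1 (primary endpoint) uses Fisher below an expected count of 5, Yates between 5 and 10, and otherwise Pearson, two-sided at 0.05. For n per arm and counts a and b, uncorrected Pearson is

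X² = (b − a)² × 2n / [(a + b)(2n − a − b)].

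| Control v Group I, n = 286 | X² | p |
|---|---|---|
| 15 v 6 | 81 × 572 / (21 × 551) = 4.00 | 0.045 |
| 14 v 6 | 64 × 572 / (20 × 552) = 3.32 | 0.069 |
| 15 v 7 | 64 × 572 / (22 × 550) = 3.03 | 0.082 |

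At 14 v 6 the smallest expected count is exactly 10, so Yates does not apply. At 315 per arm, 15 v 6 gives 0.046 and 14 v 6 gives 0.069. By exact binomial enumeration at 5% v 2%, the chance that adding or removing one case changes significance is 25% at 286 per arm and 23% at 315.

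**3. One PP exclusion.** Leaving one control case out changes 15/286 v 6/286 into 14/285 v 6/286. The smallest expected count becomes 20 × 285 / 571 = 9.98, Yates applies, and p moves from 0.045 to 0.109 (0.067 uncorrected).

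**4. One-sided misclassing with no drug effect.** Let true incidence be p in both arms, and let a fraction r of Group I cases be classed as non-cases. Observed cases are then Binomial(315, p(1 − r)) in Group I and Binomial(315, p) in control. Summing over all tables where the SAP rule is significant in favour of Group I gives:

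| Incidence p | r = 0 | r = 10% | r = 20% | r = 30% |
|---|---|---|---|---|
| 1% | 0.7% | 0.9% | 1.1% | 1.5% |
| 2% | 1.2% | 1.9% | 2.8% | 4.3% |
| 3% | 1.8% | 2.9% | 4.7% | 7.3% |
| 5% | 2.5% | 4.8% | 8.6% | 14.8% |

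The incidences span the Protocol's planning range for the control group (1 to 5%). The values of r are assumptions; the documents give none.

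**The case against.** **Scope.** A reader might infer that any of these decisions can overturn the trial's main result. The documents do not support that. The primary endpoint is any ARVI including COVID-19 in ITT, and a case moved between the suspicious, probable and confirmed classes remains an ARVI case. Confirmed cases rest largely on laboratory results. The suspicious class appears only as a row in SAP Tables 9 and 11. PP is additional under SAP 5.1 and 5.5. The Protocol's sample-size section does call PP the primary analysis population, against its own statistical section and the SAP; that conflict must be reconciled separately.

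**Much of PP is rule-based.** The Protocol lists ten exclusion criteria and a graded compliance rule, and SAP Table 1 reports exclusions by criterion. The two deviation terms may be a translation variant. This stands, and it narrows the PP gap to unlisted deviations and mainly criteria 4 and 6.

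**Size.** Any test near 0.05 turns on one case, so fragility is not evidence of bias. At 1 to 3% incidence the inflation is small in absolute terms. The Protocol's 14% refers to medical workers in the high-risk zone, not to the planning range, so larger figures at that rate should not carry the point.

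**Data in view.** SAP 5.4 mentions a small proportion of vaccinated participants, which might suggest that the rules were set with results known. The footnote gives neither an outcome nor an arm, so it does not show that.

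**Limits of any remedy.** Arm shows through preventive-medication records, since the therapy rules differ by group, and through exclusion criteria 5 and 7, which apply only to the study group. Later review also cannot recover illness that the site never recorded. Both objections stand and shape the fix.

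**Conclusion.** The gap holds and should be closed, with moderate weight. Keeping data staff apart from patient care is not masking, and neither document fixes ARVI status or judgement-based PP exclusions before the group is seen. At the top of the planning range, 20% one-sided misclassing would raise the chance of false significance in favour of the drug from 2.5% to 8.6%; at 1% incidence it goes only from 0.7% to 1.1%. These figures rest on an assumed misclassing rate, all of it in one direction, with equal true incidence. They show what the plan leaves possible, not that misclassing will occur.

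**What to change.** Add to SAP 2.3 a paragraph to this effect:

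> Participants and investigators are open-label. Before the group code is merged, the employees named in 5.1 derive ARVI yes/no with onset date, and COVID-19 class, by applying the written criteria of 3.2 to the recorded data. They also settle PP exclusions that need judgement. They work from listings with recoded numbers and without arm-revealing fields: instillation times, compliance, preventive medication and study-group-only exclusion criteria. Compliance, prohibited-therapy and study-group-only exclusions are applied by fixed rule. The list is signed and frozen, then merged with the group code.

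These staff apply written criteria; they are not asked to re-diagnose.

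In addition, use one term for the PP deviation threshold in both places in SAP 5.5, and have the sponsor state its own criterion for complicated course before the merge. A cut-off on the WHO score should not be assumed for this: the documents do not make that link, and the score is assigned at the open-label site.

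The cost is one SAP paragraph, one recoded listing and some data-handling work by staff the SAP already names. The masking is partial and does not correct open-label symptom reporting or recording at the site.

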3. EVALUATION OF EFFECTIVENESS PARAMETERS

3.1. Endpoints of the study

The primary criterion of effectiveness is the proportion of patients with acute respiratory viral infections, including COVID-19, at the end of the period of preventive administration of the drug (measurement time: 28 days).

The scientific hypothesis is that the prophylactic administration of Ingaron will lead to a decrease in the incidence of acute respiratory viral infections, including COVID-19, among adult volunteers.

The preventive efficacy of the study drug will be evaluated by the following primary and secondary endpoints.

Primary endpoint:

The proportion of patients with acute respiratory viral infections, including COVID-19, at the end of the period of preventive administration of the drug (measurement time: 28 days).

Secondary endpoints:

1. The proportion of patients with confirmed COVID-19 at the end of the period of preventive treatment of the drug (measurement period: 28 days).
2. The proportion of patients with acute respiratory viral infections, including COVID-19, at the end of the follow-up period (change period: 2 months).
3. The proportion of patients with confirmed COVID-19 at the end of the follow-up period (change period: 2 months).
4. Frequency of development of complicated course of ARVI.
5. The proportion of participants with each of the scores (0-8) according to the WHO Clinical Improvement Scale (change period: 28 days).
6. The proportion of participants with each of the scores (0-8) according to the WHO Clinical Improvement Scale (change period: 2 months).
7. Duration of symptoms of the disease of study participants who had acute respiratory viral infections, including COVID-19 (change period: 2 months).
8. The duration of the symptoms of the disease of the study participants who were infected with ARVI, including COVID-19 (measurement period: 28 days).

3.2. Registration, analysis and evaluation of effectiveness parameters

The effectiveness will be evaluated based on the data obtained during the study visits. The effectiveness assessment will include the presence of a case of ARVI, including COVID-19.

Confirmation of clinical cases of ARVI, including COVID-19:

In the following cases:

- 1) a positive result of PCR on SARS-CoV-2 RNA, regardless of the presence of clinical symptoms;
- 2) appearance of clinical symptoms of ARVI in the absence of a PCR result on SARS-CoV-2 RNA or in the case of a negative result on SARS-CoV-2 RNA, -

at any stage during participation in the study, a completion visit (Visit 3) is conducted at the end of the quarantine period (at least 14 days from the date of signing Consent for the treatment of a new COVID-19 coronavirus infection in

outpatient settings (at home) and compliance with the isolation regime or discharge from the hospital in case of laboratory confirmation of COVID-19), at which the patient returns the participant's diary and reports his condition to the doctor-researcher, transmits information about hospitalization, duration of symptoms, results of tests and performed studies.

Definition of the COVID-19 case:

Suspicious case of COVID-19

Body temperature above 37.5 ° in addition to one or more of the following signs (in the absence of other known causes that explain the clinical picture, regardless of the epidemiological history):

- Cough (dry or with scant sputum)
- Shortness of breath
- Feeling of congestion in the chest
- SpO₂ no more than 95%
- Sore throat
- Nasal stuffiness or moderate rhinorrhea
- Smell disorders or anosmia
- Ageusia
- Conjunctivitis
- Fatigue
- Myalgia
- Headache
- Vomiting
- Diarrhea
- Skin rash

Probable case of COVID-19

Body temperature above 37.5° in addition to one or more of the following signs:

- Cough (dry or with scant sputum)
- Shortness of breath
- Feeling of congestion in the chest
- SpO₂ no more than 95%
- Sore throat
- Nasal stuffiness or moderate rhinorrhea
- Smell disorders or anosmia
- Ageusia
- Conjunctivitis
- Fatigue
- Myalgia
- Headache
- Vomiting
- Diarrhea
- Skin rash

In the presence of at least one of the epidemiological signs:

- Return from cross-border travel 14 days before the onset of symptoms

- The presence of close contacts over the past 14 days with a person under surveillance for COVID-19, who subsequently became ill
- The presence of close contacts over the past 14 days with a person who has laboratory confirmed diagnosis of COVID-19
- The presence of professional contacts with persons who have a suspected or confirmed case of COVID-19

Or in combination with characteristic changes in the lungs according to computed tomography (CT), regardless of the results of a single laboratory test for the presence of SARS-CoV-2 RNA and an epidemiological history.

Also, a possible case of COVID-19 should include a clinical case in the presence of the clinical manifestations described above (fever in combination with one or more signs) with characteristic changes in the lungs according to imaging studies if it is impossible to conduct a laboratory study for the presence of SARS-CoV-2 RNA.

Confirmed case of COVID-19

A positive result of laboratory test for the presence of SARS-CoV-2 RNA using nucleic acid amplification methods or SARS-CoV-2 antigen using immunochromatographic assay regardless of clinical manifestations, or a positive result for IgA, IgM and/or IgG antibodies in patients with clinically confirmed COVID-19 infection.

In the case of ARVI symptoms characteristic of a suspicious case of COVID-19, accompanied by a negative result of PCR test, registered during or after a preventive course (during the period of participation in the study after randomization until the end of the observation period), the patient may additionally undergo a quantitative test for the presence of IgM and IgG antibodies to SARS-CoV-2 by the ELISA method for the purpose of additional verification and detection of COVID-19 cases. An additional quantitative test for antibodies to SARS-CoV-2 can be performed from the 10th to the 21st day after the appearance of the first symptom of ARVI to register the immune response of the acute phase of infection at the beginning of its development (increased IgM levels) or during high-grade response (increased IgM and IgG), considering the seronegative the period of the disease (5-7 days). The analysis is taken only in the absence of fever and a satisfactory general condition of the patient, accompanied by a favorable recovery dynamic. When interpreting the results, it is necessary to consider the probability of obtaining false positive results (for example, the presence of "cross-reacting" antibodies). If the interpretation of the results is difficult, it is allowed to conduct a repeated ELISA study using the same test systems after 5-7 days to assess the dynamics of indicators. Quantitative determination of IgM and IgG antibodies in the blood by the ELISA method will be carried out with the support of DiaLab LLC Plus."

The condition of the study participant is assessed according to the WHO standard scale of clinical improvement from 0 to 8 points at each visit, including a phone call visit. In case of registration of ARVI at the final visit 3, in parallel with the current assessment of the participant's condition, an additional assessment of the case is carried out according to the WHO scale, reflecting the maximum clinical manifestation of the disease.

WHO Clinical Improvement Scale

Assessment on the WHO scale	0	1	2	3	4	5	6	7	8
Select the appropriate score from 0 to 8	Not infected	Outpatient		Hospitalized with mild form					Died
	there are no clinical	no activit	activity restrict	hospitalized, no	hospitalized, oxygen	non-invasive lung	endotracheal	ventilation + additional	death

	or virological signs of infection	symptomatic restrictions	ions	oxygen therapy	therapy through a mask or nasal cannula	ventilation or high-flow oxygen therapy	intubation and mechanical ventilation	organ support – pressor drugs, renal replacement therapy, extracorporeal membrane oxygenation (ECMO)	
--	-----------------------------------	--------------------------	------	----------------	---	---	---------------------------------------	--	--

